1.3.2. Pharmacokinetics

Preliminary PK of the KLS-GABA co-crystal (DFL24412) has been studied in rats after administration of gelatine capsules (size 9, Torpac®: 2 capsules for each animal corresponding to 56.9 mg/kg of KLS-GABA co-crystal).

Table 1: Main Pharmacokinetic Parameters of KLS/Gabapentin Co-crystal (DFL24412) Obtained After Single Capsule Administration in Sprague-Dawley Rats (Mean \pm SD).

Test Item	C_{max} μg/mL	AUC_{tot} h·μg/mL	AUC_{0-24h} h·μg/mL	MRT h	$t_{1/2}$ h	t_{max} h
Ketoprofen	32.6 ± 18.8	$460.3^a \pm 109$	368.6 ± 102.0	11.7 ± 2.9	17.0 ± 5.5	11.1 ± 12
Gabapentin	6.7 ± 2.4	55.7 ± 8.2	50.8 ± 8.7	6.2 ± 1.3	5.5 ± 1.9	2.3 ± 1.1

A AUC_{inf} higher than 20% (24.6%) in comparison to the AUC_{0-24h} . This value should be considered with caution.

Table 2: Concentrations of Gabapentin and Ketoprofen in Brain and Plasma 24 hours Post-Administration via Oral Gavage.

Test Item	Ketoprofen in brain ng/g	Gabapentin in brain ng/g	Ketoprofen in plasma ng/mL	Gabapentin in plasma ng/mL	Brain/Plasma Ratio Ketoprofen %	Brain/Plasma Ratio Gabapentin %
KLS/ Gabapentin co-crystal	633 ± 313	320 ± 173	15046 ± 8590	386 ± 259	4.6 ± 1.7	91.5 ± 18.8

Data clearly demonstrated that gabapentin was able to cross the blood brain barrier, showing a 91.5% of brain:plasma ratio. Interestingly, the brain penetration of ketoprofen was higher compared to the administration of ketoprofen alone (0.92%).

Further details regarding the preclinical data can be found in the Investigator Brochure (IB).

1.3.3. Toxicology

Two studies in minipigs were conducted. In the first minipig study conducted CCI the dose of KLS was mistakenly multiplied by a coefficient factor of 2.25, thus resulting in a 2.25-fold dose increase (22.5 mg/kg/day instead of 10 mg/kg/day), generating an immediate onset of severe clinical signs following the administration of DFL24412.

After analysis of the study procedures and results, it was determined that the dose level that was mistakenly administered to the minipigs corresponded to a human equivalent dose (HED) of 1226 mg KLS. This is 15.3-fold higher than the first single dose proposed in Part A of this study (80 mg KLS).

A second study in minipigs was conducted CCI using the correct dose of KLS combined with gabapentin. The drug combination was administered to two groups of animals, where each group received either a low content of impurity A in gabapentin (0.04%) or a high content of impurity A in gabapentin (3.3%).

Both drug products (with low and high content of impurity A) were well tolerated. There were no mortalities or changes in clinical parameters, with the exception of some haematological changes, including decreased levels of erythrocytes, haemoglobin and haematocrit, and a slight increase of reticulocytes. These values correlated with the minimal or mild erosion/ulceration seen in the stomachs of some animals in both treatment groups.

The changes observed in this study CCI are in line with those induced by NSAIDs in animals. Oral NSAIDs mostly affect the gastrointestinal tract, liver and kidney, inducing changes in these organs when doses are exceeded, or the treatment is prolonged. The minipig is a suitable animal model for extrapolating pharmacological, pharmacokinetics and tolerability data to humans.^{23,24} The dose administered makes a fundamental difference in the tolerability of NSAIDs including ketoprofen, and this is true in animals and in humans.²⁵

The HED of KLS administered to minipigs over 1 week of continuous oral treatment is 6.8-fold higher than the dose proposed to be administered as a single dose in this clinical study (Part A, 80 mg KLS). The good tolerability at higher exposure in minipigs provides an adequate safety margin for humans, particularly for this drug type (NSAIDs) where we may have adverse effects at a certain threshold dose (the lowest effective dose significantly reduces the risk of serious adverse effects).²⁵

In conclusion, the cause of death of the minipigs in study **CCI** was clearly identified to be due to the excessive dose of KLS. In the second study in minipigs (**CCI**), the correct dose of DFL24412 was administered and was well tolerated, with only mild macroscopic and microscopic changes observed in the stomach and in some haematology parameters. Therefore, there are no concerns regarding administration of the study drug to healthy volunteers.

Further details regarding the toxicology studies can be found in the IB.

1.4. Clinical Experience

No clinical studies have been conducted to date with the co-crystal of ketoprofen, lysine and gabapentin (DFL24412). Ketoprofen and gabapentin are well known products with well described clinical experience and safety profiles.

Further details regarding the clinical data of ketoprofen and gabapentin can be found in the IB or the SmPC.

1.5. Risk/Benefit Assessment

There is no clinical data for the co-crystal of ketoprofen, lysine and gabapentin (DFL24412). All the existing clinical data refer only to ketoprofen and gabapentin.

Further information about the known and expected benefits and risks and reasonably expected AEs of ketoprofen and gabapentin may be found in the current IB.

The risk assessment of the co-crystal of ketoprofen, lysine and gabapentin (DFL24412) is based on the preclinical and studies with the co-crystal, and the preclinical studies, clinical studies and large marketing experience for ketoprofen and gabapentin conducted to date. Summaries of findings from these studies can be found in the IB. Details of these risks and the proposed strategy to mitigate/monitor these risks are detailed in [Table 3](#).

In this study, safety will be monitored closely both by subjective reporting and by objective means i.e., serial assessments of vital signs, clinical laboratory evaluations data, physical examinations, 12-lead electrocardiogram (ECG) and AE monitoring. In addition, further assessments may be performed as needed according to the Investigator's judgement. This study will be run in a Clinical Research Unit (CRU) with immediate access to hospital facilities for the treatment of medical emergencies. Participants will remain monitored in the clinic for the duration of the study period and will only be discharged from the CRU at the end of the study period if the Investigator deems it safe to do so.

In Part A, if a subject is scheduled to receive a first or second dose of a COVID-19 vaccination within 5 days prior to receiving a dose of investigational medicinal product (IMP), their dosing session will be rescheduled. In Part B, if a subject is scheduled to receive a first or second dose of a COVID-19 vaccination within 7 days prior to capsaicin exposure, their dosing session will be rescheduled.

The vaccine will be considered as a concomitant medication with no interaction that requires advice.

Table 3: Risk/Benefit Assessment

Potential Risk of Clinical Significance	Summary of Data/Rationale for Risk	Mitigation Strategy
Skin and subcutaneous tissues reactions (including reactions such as toxic epidermal necrolysis [TEN] and Steven-Johnson Syndrome [SJS])	In an analysis of two European and one US database sources to quantify the risks of SJS and TEN associated with widely used NSAIDs in US and Europe, a total of 373 cases who developed SJS or TEN as outpatients and 1720 controls were included in the International Case-Control Study. Of the 373 cases, 112 were exposed to NSAIDs (excluding aspirin). ²⁶	Subjects with significant skin allergies, pigmentary disorders, or any active dermatological conditions will be excluded. Systematic medical examinations will be performed closely throughout the trial.
Gastrointestinal disturbance (including gastrointestinal bleeding, ulceration, and perforation)	By inhibiting cyclo-oxygenases (COX) non-selectively, NSAIDs block the formation not only of pro-inflammatory, but also important gastroprotective prostaglandins; this pharmacodynamic effect is responsible for the symptomatic gastrointestinal disturbance associated with orally administered NSAIDs. ²⁷	Subjects with a clinically relevant history of gastrointestinal disorder will be excluded. Safety monitoring will be performed closely throughout the study.
Hypersensitivity	Hypersensitivity to ketoprofen, such as life-threatening asthma, urticarial and angioedema have been reported after ketoprofen treatment. ²⁸	Subjects with history of severe adverse reactions or allergies, or a history of anaphylactic reactions to prescription medications, non-prescription medications or food will be excluded. Safety monitoring will be performed closely throughout the study.
Acute interstitial nephritis	NSAIDs have been associated with the development of acute kidney injury, including acute interstitial nephritis. ²⁹ In addition, patients with renal impairment, cardiac failure or hepatic cirrhosis may show a reduction in glomerular blood flow, secondary to a reduction in intrarenal vasodilatory prostaglandin synthesis. ^{30,31}	Subjects with clinically relevant history of endocrine, cardiovascular, gastrointestinal, hepatic, or renal disorders will be excluded. Renal function will be closely monitored throughout the trial.
Cardiovascular thrombotic events	NSAIDs may cause an increased risk of serious cardiovascular thrombotic events, myocardial infarction) and stroke, which can be fatal; this risk may increase with duration of use. ³² A study showed that the estimated adjusted relative risk of heart failure associated with NSAIDs was 1.6 (95% confidence interval = 1.2 – 2.1). The relative risk	Subjects with clinically relevant history of endocrine/diabetic and cardiovascular disorders will be excluded. During the entire trial, medical examinations and the collection of vital signs will be systematically performed.

	
was greater during the first month of therapy and was independent of treatment indication. The relative risk was even higher (1.9 [1.3 – 2.8]) among patients with prior history of hypertension, diabetes or renal failure in comparison to a rather low incidence (1.3 [0.9 – 1.9]) among individuals without these conditions.³³ Furthermore, NSAIDs are associated with small, but significant, increase in blood pressure in hypertensive patients.³⁴
	
Jaundice and hepatitis	
Prospective studies show that 1% to 2% of patients taking ketoprofen experience at least transient serum aminotransferase elevations. Marked aminotransferase elevations (>3-fold elevated) occur in <1% of patients. Clinically apparent liver injury with jaundice from ketoprofen is very rare and only individual case reports have been published.³⁵
	
Only subjects who have normal range of AST, ALT, GGT and total bilirubin levels at the screening will be included. These laboratory evaluations will be closely monitored throughout the trial. Subjects with a positive result for HBsAg and anti-hepatitis C antibody (anti-HCV) at screening will be excluded. For any subject who meets the hepatic transaminase threshold criteria, a close observation, including monitoring for symptoms and hepatic function will be performed. (See Section 7.5.1.3 and Appendix 4).

COVID-19 vaccination	
No data are available on the use of ketoprofen and gabapentin in subjects who have received the COVID-19 vaccine.
 
In Part A, if a subject is scheduled to receive a first or second dose of a COVID-19 vaccination within 5 days prior to receiving a dose of IMP, their dosing session will be rescheduled. In Part B, if a subject is scheduled to receive a first or second dose of a COVID-19 vaccination within 7 days prior to capsaicin exposure, their dosing session will be rescheduled.
	
The COVID-19 vaccine will be considered as a concomitant medication.
 
All the details of the vaccine administered must be reported in the eCRF in the concomitant medication form. Any symptoms that occur during the study period will be reported in the eCRF.
 
If a subject has COVID-19 symptoms, they will be withdrawn from the study and will be tested for SARS-CoV-2 according to the current UK standard testing.

Abbreviations: ALT = alanine aminotransferase; AST = aspartate aminotransferase; COVID-19 = Coronavirus disease 2019; COX = cyclo-oxygenase; eCRF = electronic case report form; GGT = gamma-glutamyl transferase; HBsAg = Hepatitis B surface antigen; IMP = investigational medicinal product; NSAIDs = Non-steroidal anti-inflammatory drugs; SARS-CoV-2 = severe acute respiratory syndrome coronavirus 2; SJS = Steven-Johnson Syndrome; TEN = toxic epidermal necrolysis.

Important identified risks associated with Gabapentin use are:

- Abuse and dependence
- Concomitant use with opioids
- Drug rash with eosinophilia and systemic symptoms (DRESS)
- Drowsiness/dizziness

Important potential risks associated with Gabapentin use are:

- Suicidality
- Pancreatitis

Given the significantly low dose of gabapentin contained in the investigational medicinal product (IMP), the prohibition of taking concomitant drugs and the inclusion of other exclusion criteria, these risks associated with gabapentin use are not expected to occur. However, subjects will be continuously monitored so that immediate action can be taken if necessary.

2. OBJECTIVES AND ENDPOINTS

2.1. Objectives (Part A)

2.1.1. Primary Objective

The primary objective of the study is:

- To determine the single dose PK of KLS-GABA (80 mg-34 mg) compared to KLS alone (80 mg) in healthy male subjects.

2.1.2. Secondary Objectives(s)

The secondary objective of the study is:

- To determine the safety and tolerability of a single oral dose of KLS-GABA (80 mg-34 mg) compared to KLS alone (80 mg) in healthy male subjects.

2.2. Objectives (Part B)

2.2.1. Primary Objective

The primary objective of the study is:

- To determine the pharmacodynamic (PD) effects of KLS-GABA in the ID capsaicin model in healthy male subjects.

2.2.2. Secondary Objectives(s)

The secondary objectives of the study are:

- To further investigate the safety, tolerability, and PK of single oral doses of KLS-GABA and KLS alone.
- To investigate the possible relationship between plasma levels of drug and efficacy in pain reduction.

2.3. Endpoints (Part A)

2.3.1. Primary Endpoints

The primary endpoints are plasma PK concentrations and parameters of ketoprofen alone when administered as KLS and ketoprofen and gabapentin when administered as KLS-GABA, including but not limited to: area under the concentration-time curve (AUC), from zero to the last quantifiable concentrations (AUC_{0-t}), AUC from zero to infinity ($AUC_{0-\infty}$), AUC from zero to 12 hours postdose (AUC_{0-12h}), AUC from zero to 24 hours postdose (AUC_{0-24h}), AUC from zero to 36 hours postdose (AUC_{0-36h}), AUC from zero to 48 hours postdose (AUC_{0-48h}), C_{max} , t_{max} and half-life ($t_{1/2}$) in healthy male subjects.

2.3.2. Secondary Endpoints

The secondary endpoint of the study is the clinical safety data from AE reporting, 12-lead ECG, vital signs (supine blood pressure, heart rate, oral temperature), clinical laboratory evaluations (chemistry, haematology, urinalysis and coagulation) and physical examinations in healthy male subjects.

2.4. Endpoints (Part B)

2.4.1. Primary Endpoint

The primary endpoint of the study is:

- Analgesia/reduction in pain post capsaicin injection from the ID capsaicin model.

2.4.2. Secondary Endpoint(s)

The secondary endpoints of the study are:

- Subjective rating of pain from the ID capsaicin model.
- Pain score of hyperalgesia from the ID capsaicin model.
- Area and pain score of brush-evoked allodynia from the ID capsaicin model.
- Area of flare (AF) from the ID capsaicin model.
- Plasma PK concentrations.
- Clinical safety data from AE reporting, 12-lead ECG, vital signs (supine blood pressure, heart rate, oral temperature), clinical laboratory evaluations (chemistry, haematology, urinalysis, and coagulation) and physical examinations in healthy male subjects.

3. STUDY DESIGN

This is a Phase I, randomised, 2-part study to determine the PK, safety, and tolerability of single oral doses of KLS-GABA compared to KLS alone in healthy male subjects (Part A), in addition to investigating the PD effects, PK/PD correlation, safety, and tolerability of three single oral dose levels of KLS-GABA compared to three single oral dose levels of KLS alone, 300 mg gabapentin alone and placebo in the ID capsaicin model in healthy male subjects (Part B).

3.1. Part A

Part A is a randomised, double-blind, crossover group study to investigate a single oral dose of KLS-GABA compared to KLS alone, in healthy male subjects.

[figure not shown]

Figure 4: Study Design (Part A)

It is planned to enrol 12 subjects. Subjects will take part in 2 treatment periods, in which they will receive a single dose of KLS-GABA (80 mg-34 mg) or a single dose of KLS (80 mg) alone in each treatment period.

Subjects will be required to attend the CRU for a screening visit up to 28 days prior to first dosing in Treatment Period 1 to ensure they meet the inclusion/exclusion criteria and are in good general health ([Section 6](#)).

Subjects will be admitted to the CRU on Day -1 of each treatment period for a body weight assessment and will receive a dose of KLS-GABA or KLS alone in the morning of Day 1. All subjects will undergo predose safety assessments and PK blood sampling on Day 1. All subjects will remain in the CRU until Day 3 (48 hours postdose) for the collection of safety assessments and PK blood samples at multiple time points. There will be a minimum of 7 days washout period between treatment periods.

Subjects will attend a follow-up visit 5 to 7 days post the final dose after Treatment Period 2. The duration of participation for each subject is expected to last approximately 7 weeks. A detailed plan of study assessments is provided in [Appendix 1](#).

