7. SAFETY ASSESSMENTS

Baseline safety data assessments for all parts of the study will be collected predose at the nearest timepoint to dosing as shown in [Appendix 1](#) and [Appendix 2](#). The subjects will attend a follow-up visit 5 to 7 days post-discharge from the CRU for safety follow-up procedures as shown in the Schedule of Assessments ([Appendix 1](#) and [Appendix 2](#)).

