10. STATISTICS AND DATA ANALYSIS

10.1. Randomisation and Subject Allocation

Randomisation schemes will be produced by MAC Clinical Research. Separate randomisation schemes will be produced for each of study Part A and study Part B. After informed consent is obtained, subjects will be allocated to a unique screening number.

A simple randomisation scheme will be performed for study Part A, while a blocked randomisation scheme will be used for study Part B. The block size for Part B will be 16, giving 8 blocks in total.

Only subjects who comply with all the inclusion criteria, and none of the exclusion criteria, will be randomised onto the study. The randomisation number will have 5 digital numbers, with the first being the study part (1 for Part A, 2 for Part B), the second being whether a subject is a replacement (0 = original; 1 = replacement), and the last 3 being the subject number; for example, 10011 means the 11th subject originally randomised for Part A, whereas 11011 is the replacement of 10011. All screened subjects should be identifiable throughout the study.

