5. ANALYSIS PERIODS

There will be two treatment periods within Part A. Analysis phases and treatment periods:

- SCREENING analysis phase starts with sign of Informed Consent and ends with first IMP administration;
- TREATMENT PERIOD 1 analysis phase/period starts with first IMP administration within Part A and ends with second IMP administration within Part A;
- TREATMENT PERIOD 2 analysis phase/period starts with second IMP administration within Part A and ends with the end of study.

There will be one treatment period within Part B. Analysis phases and treatment periods:

- SCREENING analysis phase starts with sign of Informed Consent and ends with first IMP administration;
- TREATMENT PERIOD analysis phase/period starts first study drug administration and ends with the end of study.

Statistical Analysis Plan

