6.6.1. Adverse Events (AE)

All verbatim AE terms will be coded using MedDRA of latest version (version will be clarified in the output footnotes) and summarized by system organ class (SOC) and preferred term (PT).

A TEAE will be defined as any AE that has an onset on or after taking study drug, or any pre-existing condition that has worsened on or after taking study drug. For Part A each TEAE will be attributed to treatment period and treatment according to onset date.

The frequency and incidence of TEAEs will be summarised by SOC and PT by treatment according to treatment period and overall. Summaries will also include, but not limited to, relationship to study drug and maximum severity. The summary will be sorted by SOC and PT by frequency from the highest to the lowest. All AE data will be listed.

For each of the summaries produced at the participant level, multiple occurrences of the same event within a participant will be counted once in the summaries by SOC and PT; multiple occurrences of the same event within a participant will be counted once in the maximum severity category and/or maximum drug relationship category. If severity or relationship is found to be missing, the most severe occurrence will be imputed for that particular summary.

These summaries will also present the number of events that occurred, so multiple occurrences of the same event within a participant will all be accounted for in the maximum intensity category and maximum relationship category they were classed as.

6.6.2. 12-lead electrocardiogram (ECG)

Descriptive statistics will be calculated for absolute value and change from baseline (pre-dose) of each parameter by visit and by treatment according to treatment period and overall. Where multiple values are recorded at a timepoint for a subject, the mean of the values will be used in the summary statistics.

Statistical Analysis Plan

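### Part A counts TEAEs over windows that can differ by period, and simple randomisation of 12 men does not guarantee that the difference cancels between drugs

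*Protocol*

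**What the plan says.** Two SAP rules set the Part A observation windows.

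- SAP 5, first period: "TREATMENT PERIOD 1 analysis phase/period starts with first IMP administration within Part A and ends with second IMP administration within Part A".
- SAP 5, second period: "TREATMENT PERIOD 2 analysis phase/period starts with second IMP administration within Part A and ends with the end of study".

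SAP 6.6.1 then allocates events to drugs: "For Part A each TEAE will be attributed to treatment period and treatment according to onset date". The output is by treatment: "The frequency and incidence of TEAEs will be summarised by SOC and PT by treatment according to treatment period and overall". Neither section gives a common interval after each dose or an adjustment for time observed.

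The lengths come from the protocol.

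- **Period 1.** Protocol 3.1: "There will be a minimum of 7 days washout period between treatment periods". No upper limit is given. Protocol 1.5 allows a dosing session to be moved because of a COVID-19 vaccination, which for the second dose lengthens Period 1.
- **Period 2.** Protocol 7.5.3.1 records AEs up to the follow-up visit. Protocol 3.1 and Appendix 1 time that visit from the dose: "Subjects will attend a follow-up visit 5 to 7 days post the final dose after Treatment Period 2". Protocol 7 times it from discharge: "follow-up visit 5 to 7 days post-discharge from the CRU for safety follow-up procedures". Discharge is 48 hours after dosing.

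Protocol 10.1 assigns the sequences: "A simple randomisation scheme will be performed for study Part A". Part B, by contrast, is blocked.

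**The concern.** The Part A secondary objective is the safety and tolerability of KLS-GABA compared with KLS. Protocol 3.3 chose a crossover so that safety could be compared within subject. If the two windows differ, each man's two drugs are observed for different lengths of time. A background event late in the washout counts as a TEAE of whichever drug he took first. An event equally late after the second dose may fall beyond the follow-up visit and never be recorded.

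If more men take one drug first than the other, that drug collects more observation time and so more background events. The by-treatment TEAE table would then show a difference that has nothing to do with the drugs. The SAP avoids this elsewhere: SAP 3 limits Part A change from baseline to Days 1 to 3 of each period. TEAEs have no such limit.

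**Working it through.** The documents state no AE observation time, so there is no figure of the plan's to reproduce. The check is direct arithmetic.

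**1. Window lengths.** Let w1 be the days from dose 1 to dose 2, and w2 the days from dose 2 to follow-up.

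- w1 is at least 7 if the washout is counted dose to dose. It is at least about 9 if counted from Day 3 to the next dose, and about 10 if counted from Day 3 to the next Day -1.
- w2 is 5 to 7 by Protocol 3.1. By Protocol 7 it is 2 + 5 = 7 to 2 + 7 = 9.

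| w1 | w2 | w1/w2 |
|---|---|---|
| 7 | 5 to 7 (Protocol 3.1) | 1.0 to 1.4 |
| 9 to 10 | 5 to 7 (Protocol 3.1) | 9/7 = 1.29 to 10/5 = 2.0 |
| 7 to 10 | 7 to 9 (Protocol 7) | 7/9 = 0.78 to 10/7 = 1.43 |

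The windows can be equal, or unequal in either direction.

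**2. Subject-days by drug.** Suppose k of the 12 men take drug X first, all complete both periods, and all have the same w1 and w2.

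- Days on X = k·w1 + (12 − k)·w2
- Days on the other drug = (12 − k)·w1 + k·w2

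| w1, w2 | Split | X | Other | Ratio |
|---|---|---|---|---|
| 10, 6 | 6:6 | 96 | 96 | 1.00 |
| 10, 6 | 7:5 | 100 | 92 | 1.09 |
| 10, 6 | 8:4 | 104 | 88 | 1.18 |
| 10, 6 | 9:3 | 108 | 84 | 1.29 |
| 7, 7 | 8:4 | 84 | 84 | 1.00 |
| 7, 9 | 8:4 | 92 | 100 | 0.92 |

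**3. Chance of each split.** Take simple randomisation as an independent, equal-probability assignment for each man, so k is Binomial(12, 0.5).

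- P(6:6) = 924/4096 = 0.226
- P(7:5 either way) = 0.387
- P(8:4 or worse) = 0.388

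**4. Effect on incidence.** Assume a constant background rate r per subject-day and no drug effect. The documents give no rate, so 0.01 and 0.03 are used as a range. The chance of at least one event in a window of w days is I(w) = 1 − exp(−r·w). The spurious difference between drugs is (2k − 12)/12 × [I(w1) − I(w2)].

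At 8:4 with 10 versus 6 days:

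- r = 0.03: (4/12) × (0.259 − 0.165) = 0.032, about 3 percentage points.
- r = 0.01: (4/12) × (0.095 − 0.058) = 0.012, about 1 percentage point.

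One man in 12 is 8.3 points, so the larger figure is under half of one subject.

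**5. With a common window.** At 5 days after each dose and an 8:4 split, 8×5 + 4×5 = 60 subject-days on each drug. The ratio is 1.0 at any split when all men complete.

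**The case against.** The strongest reply is that first and second are periods, not drugs. A reader might infer that the plan favours one drug. The documents do not support that: each drug can fall in either period, so the expected effect on the drug comparison is zero over the randomisation, and exactly zero at 6:6 with common intervals. This stands. What remains is that the trial gets one split of 12 men, and cancelling on average does not correct it.

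A reader might also take Period 1 as always the longer window. Under Protocol 7 it need not be, as the table shows.

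A larger gap is tempting too. Subtracting 28 days of screening and 5 to 7 days of follow-up from a participation of about 7 weeks (49 days) leaves 14 to 16 days between doses. That treats a rounded figure as exact. Part B has no washout: 28 + 5 to 7 gives 33 to 35 days, yet the protocol says about 6 weeks (42 days), so 7 to 9 days are slack. Taking the same slack from Part A (14 − 7, or 16 − 9) leaves 7. The protocol does not plan a two-week interval.

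The plan also has partial safeguards. SAP 3 rules out hypothesis testing. TEAEs are also summarised by relationship to study drug, and all AEs are listed. Vaccinations are recorded as concomitant medication, and in-unit monitoring to 48 hours is the same in both periods. These help a reader to recognise a stray washout event, but they do not equalise the by-treatment counts.

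**Conclusion.** The point holds as a period effect that the plan leaves uncontrolled. The Part A TEAE windows can differ in either direction, and the protocol does not secure the sequence balance at which the difference cancels between drugs. The chance of 8:4 or worse is 0.39. At an illustrative 10 versus 6 days, that split gives one drug 18% more subject-days, worth roughly 1 to 3 percentage points of TEAE incidence.

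These sizes rest on equal-probability sequence assignment, all 12 men completing, one interval length for everyone, and an assumed background rate of 0.01 to 0.03 per day. If the windows come out equal, or the split is 6:6, there is no distortion. It is a modest weakness in a descriptive 12-subject table, worth mending because the remedy is cheap.

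**What to change.** In SAP 6.6.1, base the Part A by-treatment TEAE comparison on events with onset within the same interval after each dose. Five days would serve: Period 1 lasts at least 7 days, and the earliest follow-up is 5 days after dose 2 by Protocol 3.1 or about 7 by Protocol 7, so every completer is covered on either reading. Show later events in a separate row and in the listing, and keep the all-TEAE table as the overall summary.

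Two clarifications belong with it. Reconcile Protocol 3.1 and Appendix 1 with Protocol 7 on whether follow-up is timed from the final dose or from discharge. State in SAP 5 that end of study means the subject's own follow-up visit, because Protocol 13.4 defines it by the last subject.

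The cost is SAP wording and one date cut-off in programming, with no new data. The downside is that a late-onset event leaves the comparative table, though it stays in the overall table and the listing.
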